1.1 Trial Summary and Objective

To determine whether the incidence of clinically significantly abnormal plasma electrolyte levels will be different with the use of Plasma-Lyte 148 compared to intravenous fluid with current standard composition in children following kidney transplant.

1.2 Patient Eligibility Criteria

Inclusion criteria

- 1. Patients under 18 years of age at the time of transplantation with valid patient/parental consent
- 2. Patients receiving a kidney only transplant from either a living or deceased donor, in a participating UK centre

Exclusion criteria

1. Multi-organ transplant recipients

Statistical Analysis Plan

1.4 Trial Intervention

Patient screened for eligibility (during kidney transplant workup / whilst on transplant waiting list)

Discuss study with patient and or parent/guardian

Obtain informed consent from patient (if ≥16 years old) or from parent/guardian (if <16 years old) and patient assent where appropriate

Randomisation (just prior to the kidney transplant)

CONTROL GROUP

(72 patients)

Standard intravenous fluid therapy intra- and post-operatively, as required

STUDY GROUP

(72 patients)

Plasma-Lyte-148 / Plasma-Lyte-148 5% glucose intra- and post-operatively, as required

Kidney transplant operation performed as per standard practice, with fluid therapy according to the randomisation

Follow-Up Data Collection

Day 1, Day 3 and Day 7 post-transplant

Blood results*, fluid requirements, post-operative symptoms.

*Post-operative blood sampling as per standard practice (all results, up to Day 3, for the following tests will be collected: sodium, potassium, urea, creatinine, chloride, bicarbonate, magnesium, glucose, haemoglobin. The GOSH Digital Research Environment Team will assist with the collation of this data).

Up to Day 90

Date of discharge

Transplant kidney function will be obtained directly from the UK Transplant Registry, held by NHS Blood and Transplant at Day 90

Statistical Analysis Plan

1.5 Randomisation and Blinding Procedures

Eligible patients who have consented to participate in the PLUTO trial will be randomised via an interactive web response system, provided by Sealed Envelope. Participants will be randomised in a 1:1 ratio, to the intervention and control groups. Participants will be randomised on admission to hospital for the transplant, once the trial team are confident that the transplant will be proceeding. Before performing the randomisation, the team must re-confirm the consent/assent (it may have been several weeks since initial consent was provided). The eligibility criteria should also be re-checked prior to randomisation and the site name and patient weight must be known. Upon randomisation, the site will be provided with the allocation (Plasma-Lyte or Standard fluid therapy) and the participant's randomisation number, which will be used to identify participants throughout the trial. This number will take the form RXXXX where XXXX is a four digit participant number.

The randomisation will be stratified by transplant centre and patient weight (<20kg vs ≥20kg pre-transplant). Randomisation will further be balanced using blocks of varying, undisclosed sizes. The randomisation list will be produced by the trial statistician using SAS statistical software.

1.6 Sample size calculation

The sample size required for this trial is 144 participants randomised. Analysis of 76 paediatric transplants performed at Great Ormond Street Hospital between 1 January 2015 and 31 March 2018 showed that 45 children (59%) experienced hyponatraemia within the first 72 hours post-transplant when managed with 0.45% saline 5% glucose fluid (1). This was used as the baseline rate. In the Cochrane systematic review by McNab S et al. (2), a 50% reduction in risk of hyponatraemia was shown. A greater effect size is anticipated because the rate of fluid delivery to children following kidney transplant significantly exceeds maintenance requirements (3). Using the 50% effect size from the Cochrane review, the assumed incidence of hyponatraemia would be reduced to 29.5%. A two-sided test with 90% power, 5% type I error and 1:1 allocation and allowing for two formal interim analyses for harm or benefit would require 128 patients. After allowing for 10% drop out, for example if a transplant cannot proceed due to a positive cross match, the total number of participants required is 144.

2. Data Handling

2.1 CRF descriptions and data collection schedule

| Form No. | Form Title / Description of Form | Tick if Optional |
|----------|----------------------------------|------------------|
| 1 | Screening Form | |
| 2 | Eligibility assessment | |
| 3 | Baseline Characteristics | |
| 4 | Randomisation | |
| 5 | Transplant Operation | |
| 6 | Day 1 | |

Statistical Analysis Plan

| 7 | Day 2 | |
|------|-------------------------------------|-------------|
| 8 | Day 3 | |
| 9 | Fluids | |
| 10 | Medication & Blood Products | |
| 11 | Day 7 | |
| 12 | End Of Study | |
| 13 A | SAE | \boxtimes |
| 13 B | SAE Narrative | \boxtimes |
| 14 | Additional Medications (for SUSARs) | |
| 15 | SAE CTU Use | \boxtimes |
| 16 | Withdrawal | \boxtimes |

The Trial Visit Schedule shows details of assessments to be performed as follows:

| VISITS | | | | | | | | | |
|----------------------------------|-----------|----------------------|----------|-------------------------|-------------------------|-------------------------|-------------------------|---------------------------|-----------------------|
| | Screening | Baseline (Pre-Tx) | At Tx | Day 1 Post- Tx | Day 2 Post- Tx | Day 3 Post- Tx | Day 7 Post- Tx | Month 3 Post- Tx | Hospital Discharge |
| ENROLMENT | | | | | | | | | |
| Eligibility assessment | x | | | | | | | | |
| Informed consent | | Х | | | | | | | |
| Baseline Characteristics* | | | X | | | | | | |
| Re-confirm consent | | | X | | | | | | |
| Randomisation | | | X | | | | | | |
| TREATMENT | | | | | | | | | |
| Administration of trial fluid** | | | Х | Х | Х | Х | | | |
| ASSESSMENTS | i | | | | | | | | |
| Transplant Operation Data | | | Х | | | | | | |
| Blood Results*** | | Х | X | Х | Х | Х | | | |
| Blood Gas Results (venous) | | x | x | x | x | x | | | |
| Patient Weight | | Х | Х | Х | Х | Х | | | |

Statistical Analysis Plan

| Fluid Data | X | Х | Х | Х | | | |
|-----------------|---|---|---|---|---|---|---|
| Medication | | Х | Х | Х | | | |
| Data | | ^ | ^ | ^ | | | |
| Symptom | | Х | X | X | | | |
| Assessment | | ^ | ^ | ^ | | | |
| Safety | | | | | | | |
| Reporting (see | X | X | X | X | | | |
| section 13) | | | | | | | |
| Transplant | | | | | X | X | |
| Graft Function* | | | | | ^ | ^ | |
| Discharge Date | | | | | | | Х |

2.2 Procedures for recording and reporting outcomes

CRFs will be used to collect the majority of data from study entry. Screening log number or randomisation number, and participant initials will be used on all CRFs. Data will be recorded by electronic data capture (EDC). Data for this trial are also being collected via the Digital Research Environment (DRE) at Great Ormond Street and the UK Transplant Registry (UKTR) held by NHS Blood and Transplant. The DRE are collating all blood data and data will be extracted from the UKTR on donor and transplant characteristics and survival post-transplant. Prime responsibility for the complete collection of data for each centre will reside with the local Principal Investigator but may be delegated (for example to a Research Nurse). Overall responsibility for collating data from all centres will reside with the Trial Manager.

2.3 End-point Review Panel assessments/SAE Review None.

2.4 Other assessments

None.

2.5 Trial Data Management and Verification

Quality control of data entered and data cleaning will be performed by the trial data manager and will be detailed in the Data Management Plan (FRM4727). This will include performing range, data completeness and consistency checks. Once this stage is finished, the trial dataset will be declared frozen and exported from the MACRO database for final data review and validation checks by a statistician, who will raise data queries with the trial manager or data manager. Once the trial statistician, data manager, and trial manager are satisfied that all queries have been resolved, the database will be locked. The locked database will be extracted into a statistical software package and used for final analysis.

3. Detailed Analysis Plan

3.1 Interim analysis and sample size re-estimation

The trial has a traffic light system incorporated at 15 months to assess progression from the internal pilot phase to full trial. Criteria for the traffic light system are based upon

Statistical Analysis Plan

recruitment rates (both number of sites and participants) and adherence to the intervention and control. If the red criteria are met, the trial would stop at this point. Full details can be found in section 16.3 of the protocol.

The trial will use a group sequential design with O'Brien-Fleming boundaries to inform early stopping of the trial in the case of strong evidence of harm or benefit, while preserving the overall 5% type I error rate for the trial. Two interim analyses to test for harm or benefit will be conducted after 70 and 100 patients have been recruited into the trial with primary outcome data. The stopping rules will be used as a guideline, alongside the other safety data available to the DMC, and used as part of their overall assessment of the trial.

3.2 Analysis principles

The population used for efficacy analyses will be a modified intention to treat population including all randomised participants who received a transplant. Although it is a very unlikely scenario for a participant to not receive a transplant after being randomised, it would be illogical to include those participants who have not been transplanted as no outcome data would be available. Participants will be analysed according to the trial arm to which they were randomised. This will be the primary analysis for the trial.

Participants who were not transplanted will be listed with reasons for not being transplanted. The number and percentage of these occurrences will also be tabulated by trial arm. As this number is expected to be small (<14 participants, which is 10% of the total sample size) no statistical test will be conducted to test for differences between trial arms.

Participants who did not meet all the inclusion criteria and/or met the exclusion criteria will be considered as randomised in error. There is no minimum amount of treatment, of the intervention or control, required in this trial. Non-compliance is defined as any participant randomised to the standard arm who receives any Plasma-Lyte intra-operatively or post-operatively in the first 72 hours post-transplant and any participant randomised to the intervention arm who receives any other intravenous fluid intra-operatively or post-operatively in the first 72 hours post-transplant. These occurrences will be counted as protocol deviations. In addition, protocol deviations may also occur which do not involve intravenous fluid. A decision will be made for each occurrence in a blinded manner (if possible) whether it will be classified as a protocol deviation in the analysis. All protocol deviations will be reviewed and discussed by the TMG in a blinded manner (if possible) and monitored throughout the trial.

Any participant, or their parent/guardian, who withdrew consent to participate in the trial and any withdrawal of a participant by their clinician for medical reasons, will be considered as a withdrawn participant.

- If a participant withdraws their consent prior to randomisation (participants will be approached for inclusion in the trial when they are on the deceased donor transplant waiting list or in the living donor assessment stage and then consent is reconfirmed prior to randomisation), then the participant will not be included in the primary nor secondary outcome analysis as no data will be collected.
- Withdrawal from the trial post-randomisation will not result in exclusion of the data for that participant from analysis, unless the participant or their family has requested the data already collected is removed.

Statistical Analysis Plan

• If a participant is randomised but then the transplant does not proceed, the participant should be withdrawn from the trial.

Participants randomised in error, protocol deviations and withdrawn participants will be tabulated separately with reasons. A summary will also be presented showing the percentage of participants who experienced each of these (randomised in error, protocol deviations and withdrawn) and whether any participants were co-enrolled in other trials when they were also a participant in PLUTO.

Participants randomised in error, participants with protocol deviations, those withdrawn or lost to follow up will be included in the modified intention to treat analysis where possible. A withdrawn randomised participant will only be excluded if they withdrew their consent for their data to be used in the trial.

The primary outcome will also be analysed per protocol. This analysis will exclude any randomised participant who did not receive a transplant, was randomised in error, had a protocol deviation or was withdrawn from the trial.

Statistical tests will be performed to compare primary and secondary outcomes between treatment arms. This study has only been powered to detect a difference between treatment arms in the primary outcome. All analyses specified will test a superiority hypothesis.

All tests will be two-sided, p-values of less than 0.05 will be considered as evidence of a difference between treatment arms, and conditional effects will be reported. P-values will be reported to four decimal places with p-values less than 0.0001 as <0.0001. All confidence intervals presented will be 95% and two-sided. Exact confidence intervals will be used for binary data, where exact models have been used. Multiple comparisons will be performed and this may increase the probability of observing a statistically significant result by chance. No adjustments will be made to account for multiple testing. The statistical package SAS will be used to conduct analyses.

The key demographics and clinical condition of the participants will be presented for each arm of the trial to describe the cohort. In addition, a summary of transplant characteristics will be presented for each arm of the trial. A CONSORT diagram will be presented to show how participants progressed through the trial.

All analyses and accompanying tables will be presented by the treatment to which the participant was randomised. All odds, hazard and rate ratios will be presented as Plasmalyte arm versus Standard arm. A ratio which is greater than 1 indicates that the odds, hazard or rate of the event is greater in the Plasmalyte arm. 95% confidence intervals will be presented with all ratios.

P-values for regression models will be obtained by comparing models with and without the treatment term using the likelihood ratio test. In analyses where mixed models are performed, the log-likelihood will be estimated using pseudo-likelihood methods.

All analyses will be adjusted for the stratification variables (site and participant weight pre transplant: <20kg and ≥20kg) and donor type: deceased and living, as this was also felt to be an important factor which could affect the outcomes of interest. Site will be

Statistical Analysis Plan

accounted for by including a random effect and participant weight and donor type by a fixed effect in each model.

Although PLUTO is a definitive trial, the total sample size is relatively small, hence:

- In the adjusted analyses we may observe separation of data points for outcomes with lower event rates. If this occurs, we would initially drop donor type from the model. If this does not resolve the problem, then site will be removed and a fixed effects regression model adjusting for participant weight pre transplant and donor type will be used. If this does not resolve the problem, then we would additionally drop donor type from the fixed effects regression model. If this is not suitable, then an unadjusted analysis will be performed. If the initial model is a mixed logistic regression model, then if site is removed, an exact logistic regression model will be used, where computationally possible. If exact regression is not possible, then a fixed effects logistic regression model with a Firth correction to reduce bias in the parameter estimates will be used. For each analysis, table footnotes will be used to indicate the final model type and the variables adjusted for.
- It is anticipated that in some tables and frequencies, the number presented will be less than 5. It was agreed by the TMG that all data will be presented as observed within the Data Analysis Report (as this report is only shared amongst the trial teams) but within any publications, data less than 5 will be presented as <5.

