3.3 Analysis of primary outcome measures

The number and percentage of participants who experience acute hyponatraemia (defined as plasma sodium concentration <135mmol/L) within 72 hours post-transplant will be presented by trial arm and overall. This will be analysed using a mixed logistic regression model adjusting for donor type (living vs deceased donor), participant weight (<20kg vs ≥20kg pre-transplant) and transplant centre as a random effect. A superiority hypothesis will be tested and the results from the adjusted analysis will be considered the primary analysis. The adjusted odds ratio for treatment, with 95% confidence interval, will be presented from this model, with the p-value from the likelihood ratio test when including and excluding the treatment term from the model. This will be the primary analysis. The median and interquartile range of the number of each event experienced by each participant will also be presented, but no further statistical testing will be conducted on these. As outlined above, this will be analysed using the modified intention to treat population, which includes all participants randomised and transplanted. This outcome will also be analysed in the per protocol population, which additionally excludes those randomised in error, with a protocol deviation, or withdrawn from the trial.

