4.1.2 Participants withdrawn

| Table XX | Participants w | ithdrawn* | | | | |
|---|----------------------|-----------------------|---|----------------------|---|--|
| Randomisation number | Randomised treatment | Reason for withdrawal | Level of withdrawal (from treatment or follow up) | Timing of withdrawal | Is the participant included in mITT analyses? | |
| | | | | | | |
| | | | | | | |
| | | | | | | |
| *Excludes cases which were randomised but not transplanted. | | | | | | |
| mITT=modified | intention to trea | t (primary analysi | s population) | | | |

Statistical Analysis Plan

| Table XX Participants | randomised but not transplanted |
|-----------------------|---------------------------------|
| Randomisation number | Randomised treatment |
| | |
| | |
| | |

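### The per-protocol analysis of the primary outcome drops every withdrawn child with no limit on time or level, so it can discard children with 72 hours of allocated fluid and a complete outcome

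*SAP*

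**What the plan says.** Section 3.2 excludes from the per-protocol analysis any randomised child who was not transplanted or who "was randomised in error, had a protocol deviation or was withdrawn from the trial". Section 3.3 repeats this: the per-protocol population is the one "which additionally excludes those randomised in error, with a protocol deviation, or withdrawn from the trial".

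Section 3.2 defines withdrawal broadly. It covers withdrawal of consent by the child or family, and "any withdrawal of a participant by their clinician for medical reasons, will be considered as a withdrawn participant". The definition carries no time window.

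The same section says of data after withdrawal: "Withdrawal from the trial post-randomisation will not result in exclusion of the data for that participant from analysis", with an exception where the family asks for removal. For the modified intention-to-treat (mITT) analysis it adds: "A withdrawn randomised participant will only be excluded if they withdrew their consent for their data to be used in the trial".

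The primary outcome is acute hyponatraemia, "defined as plasma sodium concentration <135mmol/L) within 72 hours post-transplant". The visit schedule in section 2.1 has trial fluid from transplant to day 3, and section 1.4 shows follow-up to day 90. The listing in section 4.1.2 has a column for "Level of withdrawal (from treatment or follow up") and another for "Timing of withdrawal". The per-protocol rule uses neither.

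**The concern.** A per-protocol set should show the treatment effect in children treated as allocated. Here both the treatment and the outcome end at 72 hours. Leaving the trial after that point says nothing about adherence and takes nothing from the outcome, yet the rule deletes the child. Fluid non-compliance is already a separate exclusion ground in section 3.2, counted as a protocol deviation, so the withdrawal ground is not needed to catch it.

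The rule also sits badly with the section 3.2 bullet on data after withdrawal. That bullet speaks of analysis in general, whereas the per-protocol rule does exclude those children.

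Finally, the definition makes no exception for a medical reason that is the outcome itself. If that occurred, the child and the event would leave the analysis together. The per-protocol result stands beside the mITT result in the section 4.3 table, and a gap between the two could then come from the exclusion rule and not from the fluid.

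**Working it through.** **Rule against timeline**

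| Child | Allocated fluid to 72 h | Primary outcome | In mITT? | In per-protocol set? |
|---|---|---|---|---|
| Completes follow-up, no deviation | yes | complete | yes | yes |
| Withdraws at day 30, data may be used, no deviation | yes | complete | yes | **no** |
| Withdrawn before 72 h, data may be used, no deviating fluid | in part | complete or partial | where possible | no |
| Plasma-Lyte child given another intravenous fluid within 72 h | no | as observed | yes | no (deviation, whatever the withdrawal rule) |

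The second row is the defect, and it follows from the text alone. The first two children do not differ in adherence or in outcome data.

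**Denominators for an illustration**

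The SAP gives no number of withdrawals, so any size rests on assumed counts. I take the planned evaluable number from section 1.6, which reproduces:

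- Rates 45/76 = 0.592 and half of it, 0.296; two-sided 5%, 90% power.
- Two-proportion formula with continuity correction: 64 per arm, 128 in total, as stated. The rounded 59% gives 65 per arm. Without the correction it is 58 per arm.
- Dropout: 64/0.9 = 71.1, so 72 per arm and 144 in total, as stated.

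Assumed events: 64 × 0.59 ≈ 38 control and 64 × 0.295 ≈ 19 Plasma-Lyte.

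Crude odds ratio, Plasma-Lyte versus standard, with every child kept:

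(19/45) / (38/26) = 0.4222 / 1.4615 = **0.289**

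**Removal unrelated to outcome (late leavers)**

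The expected odds ratio does not change; only precision is lost. If 6 per arm were lost (64 to 58), fixed-sample power would fall from 92.9% to 90.3%.

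**Removal of children who had the event (possible, not stated)**

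Removing k events from one arm lowers that arm's events and its total by k:

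| k | Control events removed: (19/45) / ((38−k)/26) | Plasma-Lyte events removed: ((19−k)/45) / (38/26) |
|---|---|---|
| 1 | 0.297 | 0.274 |
| 2 | 0.305 | 0.258 |
| 3 | 0.314 | 0.243 |
| 5 | 0.333 | 0.213 |

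The direction depends on which arm loses the children. The lower rows assume that every such withdrawal falls in one arm and none in the other, which no figure in the SAP supports.

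**A repair to avoid**

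It is tempting to keep early withdrawals who already had a low sodium and drop the rest. Inclusion would then depend on the outcome. Suppose 5 of 64 Plasma-Lyte children withdraw early, 2 with an event and 3 without. Dropping only the 3 gives 19/61 (31.1%) instead of 19/64 (29.7%), and the odds ratio becomes (19/42)/(38/26) = 0.31 instead of 0.29. That swaps one selection for another.

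**The case against.** The strongest case for leaving the rule alone has four parts.

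1. **The primary analysis is protected.** The mITT analysis keeps withdrawn children unless consent for use of their data was withdrawn, and nothing in the SAP makes a decision depend on the per-protocol result. This stands and sets the weight of the point.

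2. **Excluding withdrawn participants from a per-protocol set is a common convention.** That is true, but it does not justify exclusion after both treatment and outcome have ended.

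3. **Few children will be affected.** Section 3.8 expects little missing data from withdrawal. After day 3 little is asked of families, and day-90 function comes from the transplant registry. This also stands: the numerical effect is probably small. The 10% dropout in section 1.6 cannot be used as a withdrawal rate, because its example is a transplant that does not proceed, and those children are already outside the mITT set.

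4. **Fluid deviations overlap.** A Plasma-Lyte child switched to another fluid within 72 hours is excluded as a deviation anyway. In the standard arm only receipt of Plasma-Lyte is fluid non-compliance, so the overlap is narrower there. The withdrawal ground acts alone on a small group.

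A reader might infer that the rule will systematically delete hyponatraemic children and bias the per-protocol estimate. The SAP does not support that. It nowhere says that a sodium below 135 mmol/L leads to withdrawal, and at a planned control rate of 59% the event is expected, not exceptional. The wording permits such removal; it does not predict it.

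The bullet on data after withdrawal can also be read as meant for the mITT analysis alone. It is therefore a passage to reconcile, not a flat contradiction.

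**Conclusion.** The point holds as a minor specification fault. Followed as written, sections 3.2 and 3.3 drop children with complete, adherent primary-outcome data because they left the trial after 72 hours. That conclusion needs no assumption beyond the text. Outcome-related removal is only a possibility under the medical-reasons wording.

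The size cannot be fixed from the SAP. On the assumed 64 per arm, one child with an event removed from one arm shifts the crude odds ratio from 0.289 to 0.297 or 0.274. Five, an upper-end and one-sided illustration, shift it to 0.333 or 0.213, still strongly in favour of Plasma-Lyte. Only the supporting per-protocol analysis is affected.

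**What to change.** In sections 3.2 and 3.3:

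- Limit the withdrawal exclusion to children withdrawn from allocated fluid or from the trial before 72 hours post-transplant, identified from the timing and level columns in section 4.1.2.
- Keep all children withdrawn after 72 hours, unless the family asked for their data to be removed.
- Apply one rule to every withdrawal before 72 hours, whether or not a sodium below 135 mmol/L had been recorded. If that rule is exclusion, say that removal linked to the outcome remains possible in that window and that the mITT analysis is the safeguard.
- Keep protocol deviations as their own exclusion ground, so that a child who both deviated and withdrew is still excluded.
- Say in the bullet on data after withdrawal which analysis population it governs.

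The cost is a few sentences of SAP text. The listing already provides for the items needed, and the per-protocol set can only stay the same size or grow slightly.

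### The final primary test is judged at p<0.05 after two O'Brien-Fleming interim looks, so the promised 5% overall type I error is not preserved

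*SAP*

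**What the plan says.** - SAP 1.6 sizes the trial for "A two-sided test with 90% power, 5% type I error and 1:1 allocation and allowing for two formal interim analyses for harm or benefit", giving 128 patients, or 144 after drop-out.
- SAP 3.1 adopts a group sequential design with O'Brien-Fleming boundaries. The two interim tests "will be conducted after 70 and 100 patients have been recruited into the trial with primary outcome data". The boundaries are meant to inform early stopping "while preserving the overall 5% type I error rate for the trial". The same section describes the stopping rules as a guideline for the DMC.
- SAP 3.2 sets a single criterion for all two-sided tests: "p-values of less than 0.05 will be considered as evidence of a difference between treatment arms". It adds: "All confidence intervals presented will be 95% and two-sided".
- SAP 3.3 defines the primary test (likelihood ratio test from a mixed logistic model) and its 95% interval. It names no critical value of its own.

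Nowhere does the SAP state a nominal level for the final analysis or exempt the primary outcome from the 0.05 rule. It also does not say whether the boundaries are the classical ones or come from a spending function.

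**The concern.** An O'Brien-Fleming design holds the overall error at 5% only if the last look is tested below 0.05, because part of the 5% has been used at the earlier looks. A statistician who follows sections 3.2 and 3.3 literally would judge the final primary result at 0.05 and exceed the error rate that section 3.1 promises.

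At stake is the reading of a borderline result on the only outcome the trial is powered for. A final p-value of, say, 0.046 would be evidence of a difference under 3.2 but would not cross the boundary adopted in 3.1. The 95% interval would exclude an odds ratio of 1 while the design's own rule said not to reject. The SAP gives no way to settle such a case.

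**Working it through.** **Inputs.** From SAP 1.6: control rate 59% ("45 children (59%) experienced hyponatraemia within the first 72 hours post-transplant"), intervention rate 29.5% ("the assumed incidence of hyponatraemia would be reduced to 29.5"%), two-sided 5%, 90% power, 1:1 allocation, 128 evaluable, 144 randomised. From SAP 3.1: looks at 70 and 100 with primary outcome data. Information fractions are 70/128 = 0.547 and 100/128 = 0.781; if all 144 are analysed they are 70/144 = 0.486 and 100/144 = 0.694.

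**Step 1: the plan's own sample size.** The odds ratio is (0.295/0.705)/(0.59/0.41) = 0.291, with log −1.235. On the log-odds scale

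n per arm = (1.960 + 1.282)² × [1/(0.59×0.41) + 1/(0.295×0.705)] / 1.235² = 61.6.

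The inflation factor for classical O'Brien-Fleming looks at 70/100/128 is 1.024, so 61.6 × 1.024 = 63.06, rounded up to 64 per arm, or 128. Drop-out: 128/0.9 = 142.2, which fits 144 when rounded up to 72 per arm. The stated figures are therefore consistent with a group sequential design that holds 5% overall.

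**Step 2: the boundaries that hold 5%.** Under no effect, the statistics at the three looks are jointly normal with correlation √(t_j/t_k) for j<k.

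- Classical form: find C such that P(|Z_k| ≥ C/√t_k at any look) = 0.05. For 70/100/128, C = 2.032, with bounds 2.747, 2.299 and 2.032.
- Spending form (Lan-DeMets, O'Brien-Fleming type): cumulative two-sided alpha 4[1 − Φ(2.241/√t)], with bounds solved look by look.

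**Step 3: replace the last bound by 1.960**, as section 3.2 does, and recompute the probability of crossing at any look. Steps 2 and 3 were done by recursive numerical integration.

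| Final N, form | Interim levels (two-sided p) | Alpha spent at interims | Final level needed | Overall error if final is 0.05 |
|---|---|---|---|---|
| 128, classical | 0.0060, 0.0215 | 0.0236 | 0.0422 | 0.0567 |
| 128, spending | 0.0049, 0.0209 | 0.0224 | 0.0430 | 0.0561 |
| 144, classical | 0.0039, 0.0156 | 0.0169 | 0.0439 | 0.0555 |
| 144, spending | 0.0026, 0.0135 | 0.0143 | 0.0455 | 0.0542 |

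A simulation of 2 million trials with the classical boundaries gave 0.0565 (final N 128) and 0.0554 (final N 144). With the correct final bound it gave 0.0497 and 0.0499.

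**Step 4: does the correct level cost power?** With 64 per arm and the corrected boundaries, power for 59% versus 29.5% is about 91% (pooled variance) to 94% (unpooled). No extra patients are needed.

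**The case against.** Four points can be made for leaving the text alone.

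- *The inflation is small.* This is true. For the classical form at 128 the affected case (no interim crossing, final p between 0.0422 and 0.05) has probability 0.0567 − 0.0500 = 0.0067 under no effect. By symmetry, a false claim of benefit rises from 2.5% to about 2.8%. The model and the point estimate do not change.
- *The boundaries are only a guideline.* If no interim crossing could ever stop the trial or count as a positive finding, a final test at 0.05 would hold 5%. The figures above assume that a crossing counts. That condition should be stated, but it does not rescue the text: section 3.1 says the looks test for harm or benefit, may inform stopping and preserve 5%. An advisory boundary on which the DMC may act does not give its alpha back.
- *The figure of 0.042 is the extreme.* It needs classical boundaries and a final N of 128, and the SAP fixes neither as the final information. Section 3.2 expects fewer than 14 of 144 not to be transplanted, so more than 130 may be analysed. This stands, and it is why a range is given.
- *A 95% interval is a reporting convention.* It can sit beside a stricter threshold if that threshold is stated. An unadjusted 95% interval would still disagree with the decision in the borderline zone, so the text should at least explain it.

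The sentence in 3.2 declining adjustment for multiple testing concerns multiple comparisons. It does not reconcile the general 0.05 rule with the 5% promised in 3.1.

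**Conclusion.** The SAP is wrong as written. Sections 3.1 and 3.2 contradict each other, and following 3.2 for the final primary test breaks the error rate stated in 3.1. The overall two-sided type I error becomes 5.4% to 5.7% instead of 5%, and the final level that would keep 5% is 0.0422 to 0.0455. This rests on interim looks at exactly 70 and 100, a final N of 128 or 144, classical or spending-type O'Brien-Fleming boundaries, and interim crossings counting as rejections. Only the final primary test is at issue: the interims are governed by their own boundaries. The practical effect is confined to a final p-value between the boundary and 0.05, but it concerns the trial's one powered comparison and should be settled before the final result is seen.

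**What to change.** - In 3.1, name the boundary form (classical or spending function) and what counts as full information.
- In 3.2 and 3.3, state that the primary outcome is judged at the O'Brien-Fleming final level, recalculated by alpha-spending from the actual information fractions. Give the planned value for orientation: about 0.042 to 0.043 for looks at 70/100/128.
- Report the primary odds ratio with the matching interval (about 95.5% to 95.8%, that is 1 minus the final level) or a group-sequential-adjusted one. If a 95% interval is also shown, say that it is descriptive and does not define the decision.
- Restrict the 0.05 and 95% rules to the secondary and other analyses.

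The cost is a few sentences in the SAP and a slightly stricter final threshold. The sample size in 1.6 already allows for the two looks.
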